10. SAFETY ANALYSES

Safety and tolerability of tipifarnib will be assessed based on the following:

- Adverse events
- Hematology and chemistry toxicities reported as adverse events
- Changes in vital signs including blood pressure, pulse, and temperature
- Changes in electrocardiogram results

Unless explicitly indicated otherwise, all analyses for safety will be based on the ASaT population.

The toxicity grades for laboratory tests will be based on NCI-CTCAE version 4.03 criteria. The use of blood transfusions (platelets, red blood cells) will be reported. Similar analyses will be done for selected chemistry tests: glucose, blood urea nitrogen (or uric acid), creatinine, sodium, potassium, chloride, calcium, magnesium, phosphorus, total protein, albumin, total bilirubin, alkaline phosphatase, alt, ast, gamma-glutamyl transferase, lactate dehydrogenase, bicarbonate (or total CO₂).

Protocol KO-TIP-001

Vital sign results (weight, blood pressure, pulse, respiration, and temperature) will be summarized descriptively for each scheduled protocol time point. Changes will be calculated relative to the assessments at baseline and on the first day of each cycle of therapy. Unscheduled results will be displayed in a listing.

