12.2.2 Safety and Tolerability

Safety and tolerability of tipifarnib will be assessed based on the following:

- Incidence, duration, and severity of treatment-emergent adverse events, serious adverse events, adverse events resulting in permanent discontinuation of study drug, and deaths within approximately 30 days from the last dose of study drug (or immediately before the administration of another anti-cancer treatment)
- Changes in laboratory test results
- Changes in vital signs including blood pressure, pulse, and temperature
- Changes in electrocardiogram results

Adverse events will be coded using the latest available version of the Medical Dictionary for Regulatory Activities (MedDRA). Treatment-emergent adverse events are defined as adverse events that start on or after the first dose of study drug and within approximately 30 days of the last administration of study drug. Adverse events will be summarized by the number and percentage of subjects who experienced the event, according to system organ class and preferred term. A subject reporting multiple cases of the same adverse event will be counted once within each system organ class and similarly counted once within each preferred term.

Unless specified otherwise, the denominator for these calculations will be based on the number of subjects in each cohort who received at least one administration of tipifarnib, irrespective of the total number of doses or treatment cycles administered. These conventions will be appropriately modified to calculate AE incidence rates separately for each cycle that study therapy is administered. AE incidence rates may also be calculated based on other measures of subject exposure (e.g., total number of treatment cycles administered). AEs will also be summarized by NCI-CTCAE version 4.03 severity grade and by relationship to each study drug.

Additional summaries may also be provided for SAEs, and events resulting in the permanent discontinuation of therapy. All AEs will be included in individual subject listings.

The incidence of grade 3 and 4 hematological toxicities (including neutropenia, thrombocytopenia, and anemia) will be provided by treatment cycle and across all treatment cycles. The toxicity grades for laboratory tests will be based on NCI-CTCAE version 4.03 criteria. The use of blood transfusions (platelets, red blood cells) and/or growth factor support will be reported.

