10.2. Clinical Laboratory Evaluations

As noted above, hematological adverse events Grade 3 or above based on NCI CTCAE version 4.03 criteria will be summarized by treatment cycle and across all cohorts. A similar summary will be provided for selected chemistry toxicities, including: glucose, blood urea nitrogen (or uric acid), creatinine, sodium, potassium, chloride, calcium, magnesium, phosphorus, total protein, albumin, total bilirubin, alkaline phosphatase, alt, ast, gamma-glutamyltransferase, lactate dehydrogenase, bicarbonate (or total CO₂).

The data for clinical chemistry and hematology laboratory evaluations will be presented in listings. In addition to the results, these listings will present the normal range, toxicity grade, and clinical assessment (Normal; Abnormal, but not clinically significant; Abnormal, clinically significant) associated with evaluations.

Per subject laboratory comments for hematology, clinical chemistry, coagulation, urinalysis, serum tumor burden biomarker, and serum or urine pregnancy will also be displayed in listings.

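### The SAP builds its hematology toxicity tables from reported adverse events instead of graded laboratory values and does not declare the change

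*SAP*

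**What the plan says.** Protocol 12.2.2 lists the bases for assessing safety. One of them, separate from adverse events, is "Changes in laboratory test results". The same section says: "The incidence of grade 3 and 4 hematological toxicities (including neutropenia, thrombocytopenia, and anemia) will be provided by treatment cycle". The full scope is "by treatment cycle and across all treatment cycles", and the next sentence reads "The toxicity grades for laboratory tests will be based on NCI-CTCAE version 4.03 criteria".

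SAP 10 repeats that list. Its vital-sign item, "Changes in vital signs including blood pressure, pulse, and temperature", and its ECG item match the protocol. The laboratory item does not; it has become "Hematology and chemistry toxicities reported as adverse events". SAP 10.2, the section on clinical laboratory evaluations, then states that "hematological adverse events Grade 3 or above based on NCI CTCAE version 4.03 criteria will be summarized by treatment cycle and across all cohorts". It sends the hematology and chemistry values, with normal range, toxicity grade and clinical assessment, to listings.

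The source for chemistry is less clear. SAP 10 says "Similar analyses will be done for selected chemistry tests", while SAP 10.1 and 10.2 speak of chemistry toxicities.

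SAP 14, which is reserved for changes from the protocol's methods, names two: the addition of overall survival and a PFS/DOR sensitivity analysis on a subset.

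**The concern.** Adverse event records and laboratory values are different data sources, and this protocol deliberately keeps them apart. A table built from adverse events shows the severe cytopenias that investigators chose to report. A table built from graded values shows the severe cytopenias that were measured. If the first replaces the second without notice, the tabulated rate of severe hematological toxicity depends on reporting judgment and may be too low.

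This matters for tipifarnib. Protocol 9.4 describes myelosuppression as the most common toxicity on the earlier 21-day schedule (45% at 300 mg bid) and names hematological events among the most common adverse events in this study. The one safety table by starting dose (SAP 7.5, 8 and 10.1) is also a table of adverse events, so a comparison of cytopenia between starting doses has the same dependence.

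**Working it through.** The plan gives no figure to reproduce. The check compares the texts and then counts the data left to listings.

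**Step 1: is the substitution real?** SAP 10 carries over the vital-sign and ECG items unchanged and rewrites only the laboratory item. SAP 10.2 opens by referring back to the preceding text and names adverse events as the hematology source. The overall maximum-grade summary in SAP 10.1 is likewise for laboratory-related adverse events. No table of graded hematology values is named anywhere in the SAP.

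**Step 2: can the two sources differ?** Protocol 10.4 gives three routes by which a laboratory abnormality becomes an adverse event: clinical signs or symptoms, treatment discontinuation, or medical importance in the investigator's judgment. Protocol 9.5 adds that asymptomatic laboratory findings are not dose limiting by default, so the discontinuation route will often not apply. A grade 3 or 4 count with no symptoms, no discontinuation and no judgment of importance is properly left unreported. It is then in the listing but not in the table.

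**Step 3: is the change declared?** Neither entry in SAP 14 concerns laboratory data.

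**Step 4: how much data is left to listings?** Inputs: Protocol Table 1 with footnote 17 (Day 7 visit in Cycle 1 only) and Protocol 11.2 to 11.6. The Cycle 1 Day 1 sample is taken before dosing and counts as baseline. For a subject treated for n cycles:

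post-baseline panels = 1 (Cycle 1 Day 7) + (n − 1) (Day 1 of cycles 2 to n) + 1 (End of Treatment) = n + 1

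| Cycles n (assumed) | Panels per subject | 75 subjects |
|---|---|---|
| 2 | 3 | 225 |
| 6 | 7 | 525 |
| 12 | 13 | 975 |

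This assumes that every scheduled visit takes place and that all subjects have the same n. The 75 is the planned number of evaluable subjects and does not fix the size of the ASaT population. The counts cover panels of any grade, including normal ones, so they measure listing volume and not undercount.

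**Step 5: what form would the undercount take?** If a proportion L of subjects has a grade 3 or 4 value and a share f of them has it reported as an adverse event, the table shows L × f. The documents give neither quantity. Purely as an illustration with L = 30%:

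- f = 1.0 gives 30%
- f = 0.7 gives 30% × 0.7 = 21%
- f = 0.4 gives 30% × 0.4 = 12%

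**The case against.** The strongest reply is that the protocol never says outright that the grade 3 and 4 hematological incidence comes from laboratory values. The sentence follows a paragraph on adverse events, and toxicities could mean events. That reading is possible, but the sentence directly after it concerns grading laboratory tests. Even if it is accepted, the separate laboratory-change item still has no named summary in the SAP and no declaration.

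A second reply is that the SAP wording is mixed. SAP 10 keeps the sentence on CTCAE grading of laboratory tests. SAP 10.1 promises by-cycle toxicity tables without naming a source. SAP 6 sets a laboratory-measurement condition for safety parameters, and SAP 7.1 keeps unscheduled measurements out of summary tables; both suggest that some tables of scheduled values may be intended. The shells document, which is not available here, may contain them. This stands as a limit: the SAP text names no such table, but that does not prove none will be produced. A shells document that sets layout is not the place to settle a data source.

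A third reply is that little would be hidden. An investigator may report an asymptomatic value as medically important, and Protocol 10.3 counts abnormal laboratory findings among possible adverse events. Dose modifications (SAP 8.4) and transfusions (SAP 10.3) are summarized, and every graded value is listed. This narrows the gap to severe values that were neither reported nor acted on. It does not close it: the dose-modification summary names no cause, and transfusion tables do not capture neutropenia. Protocol 12.2.2 also promised reporting of growth factor support, which SAP 10 omits.

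It can also be said that the protocol specifies no shift table. That is true. A shift table is one reasonable way to deliver the promised laboratory-change assessment, not a protocol requirement.

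**Conclusion.** The concern holds. For hematology, the SAP text moves the toxicity summary from graded laboratory values to adverse events. For chemistry, the source is ambiguous. SAP 14 declares neither. Under the protocol's own reporting rule, a severe value can be absent from the named tables while it remains in the listings.

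The size of any undercount is unknown and may be zero, because the share of grade 3 and 4 values reported as adverse events is not in the documents. The primary endpoint (ORR) and the formal secondary endpoint (TEAEs and SAEs) are unaffected, and no data are lost. This is a gap in a supporting part of the safety plan and should be corrected. The conclusion rests on reading the protocol's hematological toxicity sentence together with the laboratory-grading sentence that follows it, and on the SAP text without its table shells.

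**What to change.** - In SAP 10.2, tabulate the worst post-baseline CTCAE v4.03 grade per subject from all recorded hematology and chemistry values, by cycle and overall, in the ASaT population by cohort.
- Add a table of shifts from baseline to worst grade, to cover the protocol's laboratory-change item.
- Exempt both from the SAP 7.1 exclusion of unscheduled measurements. After Cycle 1 the only scheduled on-treatment hematology draw is Day 1 of each cycle, so a low count found between those visits would otherwise be left out.
- Keep the adverse event table beside them, and state for each toxicity table in SAP 10.1 and 10.2 whether it draws on adverse event records or laboratory values.
- Record any remaining departure from Protocol 12.2.2 in SAP 14.

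The cost is SAP wording and a few extra tables from values and grades already collected and listed. Reported laboratory toxicity rates may rise as a result.

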10.1. Adverse Events

Adverse events will be coded using the latest available version of the Medical Dictionary for Regulatory Activities (MedDRA) Version 19.0. Treatment-emergent adverse events are defined as adverse events that start on or after the first dose of study drug and within approximately 30 days of the last administration of study drug. Adverse events will be summarized by the number and percentage of subjects who experienced the event, according to system organ class and preferred term. A subject reporting multiple cases of the same adverse event will be counted once within each system organ class and similarly counted once within each preferred term.

Unless specified otherwise, the denominator for these calculations will be the number of subjects who received at least one administration of tipifarnib, irrespective of the total number of doses or treatment cycles administered. These conventions will be appropriately modified to calculate AE incidence rates separately for each cycle that study therapy is administered. AE incidence rates may also be calculated based on other measures of subject exposure (e.g., total number of treatment cycles administered).

AE durations will be calculated using all TEAEs. For AEs that are still ongoing at the end of study, we will use either death or the last contact date as the end of AE stop date for calculation the duration of AEs. Median, minimum and maximum of AE durations will be reported.

AEs will also be summarized by NCI-CTCAE version 4.03 severity grade and by relationship to study drug. Additional summaries may also be provided for SAEs, and events resulting in the permanent discontinuation of therapy. All AEs will be included in individual subject listings.

An overall view of TEAEs will be provided, which will include the total number of TEAEs, number of subjects with TEAEs, study drug-related TEAEs, Serious TEAEs, study drug-related Serious TEAEs, Grade 3 or higher study drug-related TEAEs, deaths within 30-days of administration of study-drug, and AEs leading to permanent discontinuation of study drug. Additionally, a corresponding overall view of exposure-adjusted AE incidence will be provided, which will present exposure-adjusted incidence rates (calculated as the mean number of events per treatment cycle) with corresponding 95% confidence intervals.

Summary tables will be provided which present the incidence of TEAEs by SOC and PT; and the incidence of TEAEs by SOC/PT by maximum severity (NCI-CTCAE Grades 1 through 5), overall and by cohort. Corresponding summaries for laboratory-related AEs will also be provided.

A summary of the AE durations for all TEAEs by SOC/PT will be provided.

Summary tables will be provided which present the incidence of study-drug related TEAEs and the incidence of study-drug related TEAEs with severity scores of Grade 3 or higher by SOC/PT.

Protocol KO-TIP-001

Summary tables will be provided which present the incidence of SAEs, the incidence of study drug-related SAEs, the incidence of TEAEs leading to permanent discontinuation of drug, and the incidence of TEAEs by starting dose (600 mg BID versus 900 mg BID), all by SOC/PT.

Summary tables will be provided which present Grade 3 or above chemistry and hematology toxicities by treatment cycle, fatigue (preferred term) by treatment cycle, and gastrointestinal events (SOC) by treatment cycle.

Data on adverse events will be presented in listings.

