7.2. Interim Analyses and Data Monitoring

One or more interim analyses may be conducted. The first interim analysis will be conducted to assess preliminary anti tumor activity in Cohort 2 Stage 1 patients (N=11). At this interim analysis the decision to terminate the study can be made if one or fewer responses are observed. Further interim analyses may be conducted to present the current data without requiring the application of predefined stopping rules.

Interim Analyses to present data will include all events, including but not limited to adverse events, response assessments, and study drug administration, that are recorded in the database (data cut of Sept 30, 2020 and April 10, 2020).

- Adverse Events
 - If stop date is past the cut off date
 - Remove stop date and change to 'Ongoing'
 - Have Action and Outcome = 'Not Recovered/Not Resolved'
 - Duration will be censored at the data cut off of date, death, or end of study, whichever is first
- Con Med Data
 - If stop date is past cut off date, remove stop date and change to 'Ongoing'
- Study Drug Data
 - Remove stop date if past cut off date. 'Last treatment' will be the last treatment prior to or on cut off date.

Protocol KO-TIP-001

- Any other dates past cut off
 - Remove stop date and change to 'Ongoing'
 - Blank out any information not attainable until completion of record

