7.6. Handling of Dropouts or Missing Data

Where individual data points are missing because of insufficient samples, dropouts, or other reasons, the data will be analyzed based on reduced denominators. For survival analysis, dropouts without confirming events will be treated as censored.

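### AEs still open at end of study are closed at death or an undefined last contact and summarised as complete, which mixes AE duration with follow-up length and does not match the SAP's censoring wording for data cuts

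*SAP*

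**What the plan says.** Protocol 12.2.2 makes duration part of the safety assessment: its first item is "Incidence, duration, and severity of treatment-emergent adverse events".

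SAP 10.1 sets the rule for the final analysis. On scope, "AE durations will be calculated using all TEAEs". For events still open at end of study, "we will use either death or the last contact date as the end of AE stop date". The statistics follow: "Median, minimum and maximum of AE durations will be reported". The output is a table: "A summary of the AE durations for all TEAEs by SOC/PT will be provided". The section names no censoring, no Kaplan-Meier estimate and no count of open events.

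SAP 7.2 covers presentations at a data cut ("Interim Analyses to present data will include all events") and names two cuts in 2020. Open events keep an unresolved outcome, and "Duration will be censored at the data cut off of date, death, or end of study, whichever is first". No estimator is named there either.

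The general sentence in SAP 7.6 does not fill the gap, because it is limited to time-to-event endpoints: "For survival analysis, dropouts without confirming events will be treated as censored".

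**The concern.** An AE that is open when observation ends has a known minimum duration, not a known duration. Giving it a stop date and taking a plain median treats it as resolved. The table by SOC and preferred term would then show no difference between a toxicity that cleared and one that was still present when the subject was last seen. The maximum has the same problem: if the longest recorded event is an open one, the figure is a length of follow-up.

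Open events are to be expected. AE assessment runs to about 30 days after treatment, with optional longer follow-up (Protocol Table 1, footnotes 1 and 18; Protocol 10.9). The protocol text on monitoring of subjects with AEs ends the sponsor's follow-up of non-serious AEs at database lock.

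Two things are at stake: whether a safety measure named in the protocol can be read as a duration, and whether duration tables from the 2020 data cuts can be set beside those in the final report.

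**Working it through.** The documents give no AE duration, no share of open events and no planned precision for this summary, so there is no plan figure to reproduce. The inputs below are assumptions: a true median of 14 days (for scale only) and a share c of events open, varied from 10% to 40%, with one case at 60%.

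**1. The two rules side by side.**

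| | SAP 10.1, end of study | SAP 7.2, data cut |
|---|---|---|
| Treatment of open events | given a stop date | described as censored |
| Date used | death or last contact | earliest of cut-off, death, end of study |
| Estimator | plain median, minimum, maximum | none named |

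The rules share death. They differ in the other dates and in how the event is treated, and no reason is given.

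**2. If last contact is the last AE assessment.** Each recorded duration is then at most the true one, so the plain median can only fall or stay the same.

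*Exponential case.* Let durations have rate λ and an independent cutoff have rate μ. The recorded value is the smaller of the two and has rate λ + μ. The open share is c = μ/(λ + μ), so the plain median is ln 2/(λ + μ) = (1 − c) × true median.

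- c = 10%: 0.9 × 14 = 12.6 days
- c = 20%: 0.8 × 14 = 11.2 days
- c = 30%: 0.7 × 14 = 9.8 days
- c = 40%: 0.6 × 14 = 8.4 days

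A simulation of 400,000 durations gave 12.56, 11.19, 9.77 and 8.41. The Kaplan-Meier median with open events censored was 13.95 to 13.96 throughout, which is 14.0 after rounding.

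*Common cutoff.* If every open event is closed at the same long duration and fewer than half are open, the open events all lie above the median and it does not move: the simulated plain median was 13.97 at 10%, 30% and 45% open. At 60% open it fell to 10.32, and the Kaplan-Meier median was not reached.

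*Small example.* Take four resolved events at 5, 9, 14 and 20 days and three open ones at 6, 10 and 12 days. The plain median of the seven is 10. The Kaplan-Meier curve is 6/7 = 0.857 after day 5, 0.857 × 4/5 = 0.686 after day 9, and 0.686 × 1/2 = 0.343 after day 14, so its median is 14.

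**3. If last contact is a later survival contact.** Protocol 11.7.1 has contacts about every 12 weeks after progression, possibly by phone, and Table 1 lists no AE assessment at the Follow Up Contact. An open AE would then be carried past the last date on which it was observed. If the added gap puts all open events above the median m, then m solves (1 − c)(1 − exp(−λm/(1 − c))) = 0.5, which gives m = −((1 − c)/λ) ln(1 − 0.5/(1 − c)), with 1/λ = 14/ln 2 = 20.2 days.

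- c = 10%: 0.9 × 20.2 × 0.811 = 14.7 days (14.7/14 = 1.05, about 5% too long)
- c = 30%: 0.7 × 20.2 × 1.253 = 17.7 days (17.7/14 = 1.26, about 26% too long)

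Simulation with gaps of 30 to 365 days gave 14.7 and 17.7.

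**The case against.** **Death as a stop.** An AE cannot outlast the subject, and for a fatal event death is the outcome (Protocol 10.3). Ending the duration at death is a defensible measure of duration while alive. Censoring at death in a Kaplan-Meier analysis would treat the AE as continuing afterwards and could overstate duration. This stands: the defect lies in last contact, and in not separating events ended by death from resolved ones.

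**Contradiction.** A reader might infer that SAP 10.1 and 7.2 contradict each other. They govern different occasions, and because SAP 7.2 names no estimator, its wording may mean only that the duration is cut at that date. What the documents support is an unexplained inconsistency.

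**Small consequence.** No hypothesis test, stopping rule or ORR result uses AE duration. All AEs are listed by subject, outcome is recorded (Protocol 10.8), and AEs possibly related to the drug are followed until they stabilise or the outcome is known. This limits the weight of the point but does not repair the table, which shows neither how many events were open nor how many ended in death.

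**Sparse data.** With up to about 75 evaluable subjects, many preferred terms will have few events, and repeated events within a subject are not independent. Kaplan-Meier medians for every term would be unhelpful. This also stands and narrows the fix.

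**Conclusion.** The point holds as a problem of definition and summary. SAP 10.1 gives open events a stop date and reports them as complete, so the figures blend AE duration with follow-up length. The treatment and dates also differ, without explanation, from those in SAP 7.2.

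A reader might infer that the rule necessarily shortens the reported durations. The documents do not support that. With last contact undefined, the median can be too short, unchanged or too long. The 10% to 40% shortfall at 10% to 40% open rests on exponential durations, a cutoff independent of duration, and last contact being the last AE assessment. The 5% and 26% excesses at 10% and 30% open rest on the same exponential model with a later survival contact. None of these is an estimate for this trial, whose open share is not stated.

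The effect is confined to a descriptive safety summary. ORR and the two-stage decision are unaffected. It is worth correcting because duration is named in the protocol and the change is small.

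**What to change.** In SAP 10.1:

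- Right-censor AEs not resolved at the last AE assessment, at the date of that assessment. State that a survival contact does not count as one.
- Keep death as an end of the duration while alive, say so explicitly, and report it separately from resolution.
- Report the Kaplan-Meier median where event numbers allow.
- Always report, by SOC and preferred term, the number of events ongoing and the number ended by death.

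Apply the same rule in SAP 7.2, with the data cut-off as a further limit on observation, so that data-cut and final tables can be compared.

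The cost is a few sentences and standard programming; SAP 9.2 already uses Kaplan-Meier for DOR and PFS. Some medians will be longer or not reached, and sparse preferred terms will show counts and ranges only.
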